8.1.1 Lost to Follow-Up

A participant will be considered Lost to Follow-Up (LTFU) if he/she repeatedly fails to return for/complete scheduled visits and is unable to be contacted by the investigational site. This does not apply to missed visits, where the participant misses one (1) follow-up visit but completes a subsequent one.

The following actions must be taken if a participant fails to return for/complete a required study visit:

- The site must attempt to contact the participant and reschedule the missed visit as soon as possible and counsel the participant on the importance of maintaining the assigned visit schedule and ascertain whether or not the participant wishes to and/or should continue in the study.
- Before a participant is deemed LTFU, the investigator or designee must make every effort to regain contact with the participant (where possible, 3 telephone calls and, if necessary, a certified letter to the participant's last known mailing address or local equivalent methods). These contact attempts should be documented in the participant's medical record and source documents.
- Should the participant continue to be unreachable, he/she will be considered LTFU effective the date of the final failed contact attempt.

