1.2 Schedule of Activities

Procedure	Screening	Index Procedure Day 1	Study Visits				
			Follow-Up Visit 1 1 month (±7-days)	Follow-Up Visit 2 3-months (±15-days)	Follow-Up Visit 3 6-months (±15-days)	Follow-Up Visit 4 12-months (±30-days)	Unscheduled
In-Clinic Visit or Telephone Visit (Screening must be in-clinic visit)	x	x	x	x	x	x	x
Informed Consent	x						
Eligibility	x						
Demographics	x						
Physical Examination	x						
Medical History	x						
Dialysis History	x						
Procedure Overview		x					
Study Device Details		x					
Hemodialysis Catheter Assessment			x	x	x	x	x
Dialysis Session Logs			x	x	x	x	x
Device Deficiencies / Malfunctions			↔				
Re-Intervention Assessment			↔				→
Adverse Event Assessment			↔				→
Protocol Deviations		↔				→	

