7.4 Participant Follow-Up

7.4.1 Follow-Up Intervals and Methods

Enrolled participants will have follow-up visits at 1-month, 3 months, 6-months, and 12-months via either in person visit or telephone call. For participants into whom the Pristine™ Catheter was introduced during the index procedure, but procedure success was not achieved, only the procedure eCRF will be collected and limited to the collection of safety events and interventions for up to 30 days.

Follow-up windows will be calculated from the index procedure date. Refer to Section 1.2 for an overview of follow-up window time frames and requirements for each visit. The

following data will be collected and documented on the appropriate eCRF for each follow-up unless otherwise specified for treated participants:

- Hemodialysis Catheter Assessment:
 - Document how the participant has been receiving hemodialysis and document the date of the participant's last HD session.
- Dialysis Session Blood Flow Rate:
 - If dialyzing through the Pristine™ Catheter, document the reported dialysis sessions and details such as date of dialysis session, average blood flow rate, number of line reversals, and length of dialysis session.
- If Needed:
 - Documentation of any protocol deviations that have occurred since the last follow-up.
 - Documentation of occurrence and / or status of AEs since the last follow up (refer to Section 9).
 - Any catheter reinterventions the participant has undergone since the prior follow-up.

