Legally Authorized Representative (LAR)	Individual or judicial or other body authorized under applicable law to consent, on behalf of a prospective participant, to the participant’s participation in the clinical investigation. “Legally designated representative” or “legally acceptable representative” are other terminologies used under national regulations for “legally designated representative”.
Line Reversals	Reversal of lumens of the catheter to allow for completion of HD treatment.
Lost to Follow-Up (LTF)	A participant may be considered LTF if the investigation site team members are unable to locate the participant despite three documented attempts to notify the participant via telephone and, if necessary, a certified letter to the participant’s last known mailing address or local equivalent methods. This does not apply to missed visits, where the participant misses one of the follow up contact time points but completed a subsequent one (when participant misses two consecutive follow-ups and is unable to be contacted with the documented attempts outlined before, the participant may be considered LTF and withdrawn from the clinical investigation). The site should also contact the HD center to ascertain the participant’s status. Before the site considers a participant LTF, written agreement should be obtained from the Sponsor.
Malfunction	Defined as a failure of a medical device to perform in accordance with its intended purpose when used in accordance with the IFU or CIP.
Mild AE	Awareness of a sign or symptom that does not interfere with the participant’s activity or is transient and is resolved without treatment or additional sequelae.
Moderate AE	Interferes with the participant’s usual activity and / or requires additional intervention and / or treatment and may have additional sequelae.
Monitoring	Act of overseeing the progress of a clinical investigation and to ensure that it is conducted, recorded, and reported in accordance

Term	Definition
	with this CIP, written procedures, applicable standards, and the applicable regulatory requirements.
Not Related AE	An AE is not related if it is determined that there is no plausible association.
Operator	Primary individual responsible for conducting the index procedure.
Point of Enrollment	Time at which, following recruitment and before any clinical investigation-related procedures are undertaken, a participant signs and dates the ICF.

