### 5.3 Secondary endpoints

#### 5.3.1 Rate of freedom from catheter-related bloodstream infection (CRBSI) defined by 2019 KDOQI Guidelines for CRBSI.

##### Binary Analysis

Subject will be considered as having CRBSI for a given visit if the subject has experienced device-related bloodstream infection prior to the upper limit of visit window for the visit:

- **AE CRF Page:** AE start date  $\leq$  upper limit of the visit window AND Relationship to study Device: Equals 'Related' or 'Likely Related' AND Was event infectious: Equals Yes AND Select Type of Infection: Equals Blood Stream and Were there clinical manifestation and at least 1 positive blood culture with no apparent source: Equals Yes; subject will be considered as a failure at the AE date

If the subject has not become failure and experience one of the following events prior to the lower limit of visit window, then subject will be considered as non-evaluable at the earliest occurrence of following event dates.

- Catheter has been removed due to Kidney Transplant, Transferred to AVG/AVF, Peritoneal Dialysis, Withdrawal of Care, or Other reasons

***Hemodialysis Catheter Re-Interventions CRF page:*** Catheter removal Equals Yes AND Reason for

*catheter removal Equals: Kidney Transplant, Transferred to AVG/AVF, Peritoneal Dialysis, Withdrawal of Care, or Other*

OR

- Subject has discontinued from the study.

Else subject will be considered as a success (freedom from CRBSI) for a given visit.

The rate of freedom from CRBSI will be reported with 95% confidence interval from the exact binomial method. The analysis will be performed on the mITT population through 1-month, 3-months, 6-months, and 12-months.

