### **Kaplan-Meier (KM) Analysis**

KM analysis will be used to estimate the time from the date of index procedure to the first CRBSI event and to determine the rate of freedom from CRBSI at 1-, 3-, 6-, and 12-months. CRBSI is considered as the event.

Subjects that have not reached CRBSI (event) will be censored or considered event free as described below.

- If the subject has experienced following events, subject will be censored at the earliest date of those events.
  - Catheter has been removed due to Kidney Transplant, Transferred to AVG/AVF, Peritoneal Dialysis, Withdrawal of Care, or Other reasons
  - Subject has discontinued from the study.

Note: How to assess the above events has been described in **Error! Reference source not found.** the Binary Analysis section.

- All the other subjects will be considered event free and will be censored on visit day (visit day can vary from lower limit to upper limit of visit window).

This endpoint will be evaluated on the mITT populations through 1-month, 3-months, 6-months, and 12-months.

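### If the SAP dates loss to follow-up at the final failed contact, unknown outcomes count in the device's favour in five secondary endpoints

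*Protocol*

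**What the plan says.** Protocol 8.1.1 ties the contact attempts to a missed visit: "The following actions must be taken if a participant fails to return for/complete a required study visit". If the participant stays unreachable, "he/she will be considered LTFU effective the date of the final failed contact attempt". Protocol Appendix A describes loss as arising "when participant misses two consecutive follow-ups and is unable to be contacted with the documented attempts outlined before". It also asks the site to check with the dialysis center and to obtain the sponsor's written agreement first. Under protocol 8.1, no further data are collected once a participant discontinues.

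On timing, "Follow-up windows will be calculated from the index procedure date" (protocol 7.4.1). The schedule allows ±7 days at month 1, ±15 at months 3 and 6, and ±30 at month 12.

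SAP 5.3.1, 5.3.2 and 5.3.4 to 5.3.6 share one binary scoring rule. A recorded failure up to the window's upper limit is a failure. The non-evaluable category begins "If the subject has not become failure and experience one of the following events prior to the lower limit of visit window", the events being catheter removal for a listed reason or discontinuation from the study. Everyone else is a success. No rule requires that the visit took place or that status was learned.

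For the same events the KM analyses say "subject will be censored at the earliest date of those events". All other event-free participants are censored on their visit day. The SAP does not say which date is the discontinuation date of a lost participant.

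**The concern.** The non-evaluable and censoring rules exist so that unknown outcomes are not credited to the device. For loss to follow-up they act too late. Loss is discovered through a missed visit and dated after it, whereas the binary rule excludes only participants who discontinued before that visit's window opened.

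Five endpoints are involved: freedom from CRBSI, freedom from device- or procedure-related adverse events, participant survival, catheter survival and patency. The error runs in one direction, and lost participants stay in the denominator, so the exact intervals are also too narrow. Protocol section 3 says the study's information is intended for the device's labeling, so these rates may be read outside the study report.

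**Working it through.** The documents give no figure for how lost participants affect the secondary rates, so there is none to reproduce. The check has two parts: applying the rules to dates, then sizing the effect under stated assumptions.

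**Window limits** (months taken as 30, 90, 180 and 365 days):
- Month 1: 30 − 7 = day 23.
- Month 3: 90 − 15 = day 75. The upper limit, 90 + 15 = 105, matches the SAP's day 105.
- Month 6: 180 − 15 = day 165.
- Month 12: 365 − 30 = day 335.

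**Rules applied** to a participant with no recorded failure and no listed removal, using the final failed contact as the discontinuation date:
- Misses month 1, dated day 40 or 50: success at month 1, non-evaluable from month 3.
- Misses month 3, dated day 95 to 130: success at month 3, non-evaluable from month 6.
- Misses month 6, dated day 190 to 220: success at month 6, non-evaluable at month 12.
- Misses month 12, dated day 360 to 400: success at month 12.

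If loss is declared only after two consecutive misses ("when participant misses two consecutive follow-ups and is unable to be contacted"), the participant is a success at both. A participant who misses only month 12 may never meet the loss definition, but is still a success because nothing places a discontinuation before day 335. The KM rule for such a participant refers to a visit day that does not exist.

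**Size at month 12.** Assume a constant hazard, a fraction p lost just after day 180, and loss unrelated to outcome. Let S be the true 12-month event-free rate, so S(180) = S^(180/365). For S = 50%, 70% and 85%, S(180) = 71.0%, 83.9% and 92.3%.

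Under the SAP rule, lost participants who were event-free at day 180 are successes:

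reported = (1 − p) × S + p × S(180)

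Example, p = 10% and S = 50%: 0.9 × 0.500 + 0.1 × 0.710 = 52.1%.

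If event-free lost participants are instead dropped while earlier failures stay in:

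reported = (1 − p) × S / (1 − p × S(180))

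Same example: 0.450 / (1 − 0.071) = 48.4%.

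| p | True S | SAP binary rule | Event-free losses dropped | KM at last known status |
|---|---|---|---|---|
| 10% | 50% | 52.1% (+2.1) | 48.4% (−1.6) | 50% |
| 10% | 70% | 71.4% (+1.4) | 68.8% (−1.2) | 70% |
| 10% | 85% | 85.7% (+0.7) | 84.3% (−0.7) | 85% |
| 15% | 50% | 53.2% (+3.2) | 47.6% (−2.4) | 50% |
| 15% | 70% | 72.1% (+2.1) | 68.1% (−1.9) | 70% |
| 15% | 85% | 86.1% (+1.1) | 83.9% (−1.1) | 85% |

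A simulation with 142 participants under the same assumptions gives 52.0, 71.4 and 85.7% at p = 10%, and 53.0, 72.2 and 86.1% at p = 15%. KM under the SAP rule carries the same bias when the censoring date falls at or after the readout day, and less when it falls earlier.

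**Earlier loss.** With 10% lost after month 1 (S(30) = 94.4%), a true 6-month rate of 71.0% reads 0.9 × 0.710 + 0.1 × 0.944 = 73.3%.

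**Interval width.** Suppose 21 of 142 are lost (15%), none with an earlier failure, and 97 of the 121 observed are successes. Treating the lost as non-evaluable gives 97/121 = 80.2% (95% CI 71.9 to 86.9, width 15.0 points). The SAP rule gives (97 + 21)/142 = 83.1% (75.9 to 88.9, width 13.0). The 2.9-point gap is a difference between two scorings, not a bias against a known truth.

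**The case against.** The strongest reply has five parts.

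- **The date is inferred.** The SAP does not define the discontinuation date, and its derived-data specification (Appendix 2) is not among the text available. This stands, so the point about dating is conditional. The success default does not depend on it for someone who misses only month 12.
- **A missed visit is not always an unknown outcome.** Follow-up is directed to the dialysis center as well as the participant, participants dialyze three times a week, outside records are to be requested for treatment-related complications, and Appendix A adds a check with the center before loss is declared. This will recover some outcomes, but the scoring does not depend on whether anything was learned.
- **The effect is small and assumed.** No loss rate after month 3 is given; the only figure is 15% total attrition through 90 days. The inflation lies within sampling error at n = 142 (approximate 95% half-width 5.9 points at 85% and 8.2 at 50%). This stands as to size. However, sampling error is symmetric and appears in the interval, whereas this error has one direction and does not.
- **No decision depends on it.** The secondary endpoints are descriptive. This stands.
- **Dropping lost participants from the binary rate creates an opposite bias of similar size.** The table confirms it, so the remedy has to rest on KM.

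A reader might go further and infer that every lost participant is scored a success. The documents do not support that: earlier failures remain failures, earlier listed removals are non-evaluable, and KM censors rather than scores. Technical success is settled at the index procedure. The primary endpoint has its own exposure rule in SAP 5.2.1 and is outside this point.

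**Conclusion.** The concern holds in a limited form. If the protocol's effective date serves as the discontinuation date, a lost participant without an earlier failure or listed removal is a binary success at the missed visit or visits. KM credits unobserved time as event-free up to that same late date. Independently of the loss definition, a participant who misses only month 12 is a binary success by default.

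The effect favours the device by about 0.7 to 3 points at month 12. This rests on assumptions that the documents do not supply: 10-15% lost after month 6, true rates of 85-50%, constant hazard, and loss unrelated to outcome. It would be larger if lost participants do worse. No hypothesis test changes, but the reported rates and intervals do.

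**What to change.** Amend SAP 5.3.1, 5.3.2 and 5.3.4 to 5.3.6:

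- **KM:** for participants lost to follow-up, or missing the visit with no later contact, censor at the last date on which catheter and adverse-event status was confirmed by the participant, the dialysis center or records. Make KM the main estimate for these rates.
- **Binary:** count a success only if status was confirmed in or after the visit window. Report the number with unknown status at each visit.
- **Label the binary rate as supportive.** Dropping event-free losses while keeping earlier failures biases it downward, by about 0.7 to 2.4 points under the assumptions above.

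Protocol 8.1.1 can keep the final failed contact as an administrative date.

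The cost is a short SAP edit and one derived date, obtainable from visit and contact records. Rates become slightly less favourable and binary denominators smaller.

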9 ADVERSE EVENTS AND DEVICE DEFICIENCIES

9.1 Definitions of Events

9.1.1 Adverse Events (AEs)

An AE is defined as any untoward medical occurrence, unintended disease or injury, or untoward clinical signs (including abnormal laboratory findings) in participants, users or other persons, whether or not related to study device [ISO14155:2020(E)].

Pre-existing conditions should be considered as part of the participant's medical history and should not be reported as an AE unless there is a substantial increase in severity or frequency of the condition. Likewise, planned hospital visits and/or hospital stays should not be considered as adverse events. Exacerbation of an existing condition should be reported as an AE if the event meets the protocol definition of an AE.

The clinical course of the event will be followed according to accepted standards of medical practice until the event resolves, stabilizes, or in the opinion of the Investigator, is no longer considered clinically significant. The Investigator must supply the Sponsor with information concerning the follow up and/or resolution of the AE.

9.1.2 Serious Adverse Events (SAEs)

A serious adverse event (SAE) is defined by ISO 14155:2020 and/or 21 CFR 803.3 as an adverse event that:

- a. Led to death;
- b. Led to serious deterioration in health that resulted in life-threatening illness or injury, resulted in permanent impairment;
- c. Required inpatient hospitalization/prolonged hospitalization, or resulted in medical/surgical intervention to prevent life-threatening illness/injury or permanent impairment; or
- d. Led to fetal distress, fetal death, or a congenital abnormality or birth defect.

9.1.3 Adverse Device Effect (ADE) / Serious Adverse Device Effect (SADE)

An adverse device effect (ADE) is defined as any adverse event that is considered to be related to the use of an medical device. This definition includes any event resulting from insufficiencies or inadequacies in the instructions for use, deployment, implantation, or

operation or any malfunction of the investigational device (study device) and includes any event that is a result of a user error.

A serious adverse device effect (SADE) is defined as an ADE that has resulted in any of the consequences characteristic of an SAE.

9.1.4 Unanticipated (Serious) Adverse Device Effect (UADE/USADE)

An unanticipated (serious) adverse device effect (UADE/USADE) is any (serious) adverse device effect on health or safety or any life-threatening problem or death caused by, or associated with, a study device, which by its nature, incidence, severity, or outcome has not been identified in the current instructions for use and/or current version of the risk analysis report, or any other unanticipated serious problem associated with a device that relates to the rights, safety or welfare of participants.

UADEs/USADEs will be reported to FDA as required by 21 CFR Part 822 and to the appropriate governing body per ISO 14155:2020.

9.1.5 Device Deficiencies

The Investigator will record a device deficiency if a device used in the study procedure failed to meet its performance specifications whether due to mechanical failure, malfunction, or defect. Device deficiencies also include use errors and inadequate labeling. This applies to: devices used to treat the participant, or devices in which the package was opened, but the device was not used for treatment, or devices with which treatment was attempted, but the device did not remain through the entire study procedure/period.

All mechanical failures, malfunctions, missing components, and defects of the study devices will be recorded on the appropriate Case Report Form and will be promptly reported to the Sponsor. The device(s) should be returned to the Sponsor as outlined in the site's regulatory binder.

If the device deficiency was associated with an AE, the reporting provisions for AEs, ADEs, SAEs, SADEs and UADEs/USADEs apply.

Reported deficiencies will be investigated and reported under 21 CFR part 803 Medical Device Reporting by the Sponsor if necessary. The site may be contacted to provide additional information to allow the Sponsor to conduct a thorough investigation.

It is the responsibility of the Investigator to notify the IRB of such device deficiencies in accordance with the local IRB's requirements.

9.2 Severity of Adverse Events

Each AE shall be assessed for its severity, by the Primary Investigator according to the criteria below.

Table 2: Severity of Adverse Event

Severity Rating	Description
Mild	Event, signs, or symptoms that do not interfere with the participant's daily activity, are usually considered self-limiting, can be treated with non-prescription type medications, and do not require medical intervention
Moderate	Event may interfere or cause low level inconvenience with the participant's daily activity. Requires medical intervention and/or treatment; however, unlikely to require hospitalization or be considered potentially life-threatening in nature
Severe	Event may cause significant discomfort to the participant and/or interferes with the participant's daily activity. Requires medical intervention and/or treatment to preclude a permanent impairment; may be life threatening and/or require hospitalization

9.3 Relationship of Adverse Event to Device(s)/Procedure

Each AE will be assessed for its relationship to the study device or procedure according to the following guidelines.

- A. Assess each AE for its relationship to the device or procedure.
 - Device Related: This category should be restricted to AEs directly attributable to the study device used from the placement procedure of the Pristine™ Catheter to completion of all follow-up for that patient.
 - Procedure Related: A procedure includes any study-related activity performed during the index procedure of the Pristine™ Catheter.
- B. The following categories shall be used for assigning the certainty of the relatedness.

Table 3: Relationship of Adverse Events

Relatedness	Description
Not Related	Event is independent of study intervention and/or evidence exists that the event is related to another etiology. There must be an alternative etiology documented by the clinician.
Unlikely Related	Event in which the temporal relationship to study intervention makes a causal relationship improbable (e.g., the event did not occur within a reasonable time of the study device use) and in which underlying disease provides plausible explanations (e.g., the participant's clinical condition other concomitant treatments).
Likely Related	Event in which there is evidence to suggest a causal relationship and the influence of other factors is less likely. The event occurs within a reasonable time after use of the study device and is less likely to be attributed to concurrent disease.
Related	Event in which there is clear evidence to suggest a causal relationship and other possible contributing factors can be ruled out. The event occurs in a plausible time relationship to use of the study device and cannot be explained by concurrent disease.

